EXPECTED RESULTS

Following completion of the study procedure administration protocol with the Erchonia® HLS™, it is anticipated that compared with baseline, subjects will show a reduction in tinnitus symptoms at study endpoint evaluation.

HISTORY OF THE CLINICAL STUDY

WIRB PRO NUM: 20182570: A double-blind, placebo-controlled randomized evaluation of the effect of the Erchonia® FX-635™ on the relief of tinnitus symptoms

DEVICE DESCRIPTION

The Erchonia® HLS Laser will be self-administered by the subject at home, for a total of 56 treatment administrations: Daily administration for 8 consecutive weeks. Each HLS administration will last a total of 10 minutes.

The Erchonia HLS Laser is a hand-held single diode, variable hertz laser that is portable, self-contained, lightweight, and battery operated.

The Erchonia HLS Laser emits a 640 nanometer (nm) wavelength with a tolerance of ± 10 nanometer. The diode is classified by the Center for Devices and Radiological Health (CDRH) as Class II laser diode in accordance with IEC 60825-1, compliant to 21CFR1040 via Laser Notice#50.

An internal battery that is recharged using an external inductive charging base powers the laser. The internal battery powers the specially created and patented electronic diode that emits a $<10\text{mW}$ red laser beam.

The HLS Laser has the following specifications:

Power	7.5 mW ± 1.00 mW
Wavelength	640 nm ± 10 nm
Waveform	Variable Hertz
Joules	4.5 Joules per treatment administration
Energy Source	Single electronic diode, with patented optics

Power Supply	100-240 V ac; 50-60 Hz electrical outlet, lithium-ion Polymer battery
Duty Cycle	50%
Energy Delivery	Handheld treatment probe
Treatment Time	10 minutes
Target Size	Line pattern, manually scanned over area of treatment

DEVICE SPECIFICATIONS

Figure 1 below contains an image of the Erchonia HLS Laser, and a description of the system components follows.

Figure 1: The Erchonia HLS Laser

#1 POWER BUTTON (ON/OFF)

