
JUSTIFICATION FOR THE CURRENT CLINICAL STUDY

Tinnitus is a chronic problem affecting about one in every ten Americans. The persistent perception of sound is not only annoying and bothersome, but can affect multiple aspects of an individual's life, disrupting communication and sleep, and causing emotional and social disturbances such as anxiety and depression. At present, there is no cure for tinnitus and most treatment or management options are of limited short-term benefit restricted to the time of application. Low level laser therapy, such as through application of the Erchonia HLS™ Laser, has been shown through numerous prior trials and FDA clearances to effect positive change in numerous areas, including symptom perception arising from neurocognitive disruptions through its inflammatory reduction and neuromodulation properties. Therefore, it follows that application of Erchonia LLLT may help to alleviate the severity of tinnitus symptoms, providing a simple, non-invasive, safe, effective and side-effect free alternative therapy to reducing the severity of symptoms of tinnitus in affected individuals.

STUDY DESIGN

This pilot study is a non-blinded, two-group evaluation of the effect of the Erchonia® HLS™ on providing relief from the symptoms of tinnitus.

SUBJECT GROUPS

There will be two subject groups (Group A and Group B) in this pilot study. All subjects in both groups will be test subjects; that is, all study subjects will receive the active Erchonia® HLS laser device. The only difference between subject groups will be the anatomical area(s) where the Erchonia® HLS laser device is applied.

NON-BLINDED DESIGN

This pilot study will be non-blinded, such that both subjects and the investigator(s) will be aware that they are receiving the study procedures with active (true) Erchonia® HLS laser device.

NON-RANDOMIZED

As this pilot study wherein, all subjects receive the active procedure administrations, this is a non-randomized study design. The Investigator will assign 5 subjects to Group A and 5 subjects to Group B.

SUBJECTS

Recruitment

Subjects will be recruited from among the Principal Investigator's/test site's pool of patients who are currently being treated for, or who are seeking treatment for the symptoms of tinnitus, or from response to the following recruitment materials.

- a) Flyer

WANTED

**ADULTS WITH TINNITUS ONGOING
OVER THE LAST 6 MONTHS FOR A
CLINICAL STUDY OF THE EFFECTS OF
LOW LEVEL LASER LIGHT ON

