A subject who satisfies any of the following criteria will be excluded from study participation:

- Objective tinnitus
- Atonal, pulsatile, intermittent, or occasional tinnitus
- Severe or profound hearing loss in one or both ears
- Current or prior surgically removed acoustic neuroma
- Consistent use of any of the following drugs known to cause or increase tinnitus (primarily ototoxins) within the past 30 days:
 - ✓ NSAIDS (motrin, naproxen, relafen, etc)
 - ✓ aspirin (exceeding 300mg per day) and other salicylates
 - ✓ Lasix and other "loop" diuretics
 - ✓ "mycin" antibiotics such as vancomycin
 - ✓ quinine and related drugs
 - ✓ Chemotherapy agents such as cis-platin
- Acute or chronic vertigo/dizziness
- Ménière's disease
- Prior stapedectomy
- Prior mastoidectomy
- Auditory nerve tumor (acoustic neuroma), current or surgically removed in the past
- Active infection/wound/external trauma to the areas to be treated with the laser
- Medical, physical or other contraindications for, or sensitivity to, light therapy
- Pregnant, breast feeding, or planning pregnancy prior to the end of study participation
- Developmental disability or cognitive impairment that in the opinion of the investigator would preclude adequate comprehension of the informed consent form and/or ability to record the necessary study measurements

INCLUSION CRITERIA PART 2

- Total THI score is **38 (Grade 3) or greater.**
- Numerical Rating Scale (NRS): Tinnitus Annoyance is **40 out of 100 or greater.**
- Numerical Rating Scale (NRS): Tinnitus Loudness is **40 out of 100 or greater.**

SUBJECT GROUP ASSIGNMENT

A fully qualified subject is assigned by the investigator to Procedure Group A or to Procedure Group B.

PRE-PROCEDURE EVALUATION PHASE

The pre-procedure evaluation phase commences following successful study qualification, on the same day or another day. During pre-procedure evaluation, the following is recorded over videoconference or telemedicine:

BASELINE VARIABLES

- Tinnitus Variables
- Medication and Treatment

- Subject Demographic

[figure not shown]
PROCEDURE ADMINISTRATION PHASE

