8 WEEK EVALUATION: STUDY ENDPOINT

Following 8 weeks of study procedure administrations with the Erchonia® HLS™, the following will be recorded over videoconference or telemedicine with the site investigator and subject as outlined in the STUDY TEST BATTERY section above. These recordings will form the study endpoint data set from which change from baseline will be evaluated with respect to assessing study outcome.

- Tinnitus Handicap Inventory (THI)
- Numerical Rating Scale (NRS): Tinnitus Loudness
- Numerical Rating Scale (NRS): Tinnitus Annoyance
- Subject Satisfaction With Study Outcome
- Adverse Events Evaluation

ADVERSE EVENTS

At any time throughout the duration of the clinical trial that is necessary, any and all potential adverse events reported by a subject will be reported to the investigator and will be recorded on the case report form, and subsequently evaluated by a suitably qualified independent reviewer for determination of relationship to the study treatment and whether or not any corrective action needs to be taken. All potential adverse events recorded will be appropriately reported to the governing IRB, as applicable.

It is unlikely and not expected that any adverse events will result from implementation of this clinical study protocol. Prior clinical trials using low level laser light have not typically yielded any adverse events or reactions. However, potential adverse events that may feasibly occur from application of

the Erchonia® HLS™ include, but are not necessarily limited to: skin irritation, discoloring, rash, indentations and infection.

PRIVACY AND CONFIDENTIALITY

Records for each subject in this clinical study will be maintained in separate files in a locked filing cabinet at the respective test site. The investigator at the test site will be responsible for ensuring that all records for a subject pertaining to his or her participation in the clinical study are maintained in the subject's file at all times other than when information is being recorded on them.

Copies of all subject case report forms will be made and supplied to Regulatory Insight, Inc. and Erchonia Corporation. Regulatory Insight, Inc. and Erchonia Corporation will maintain these copies in a separate clinical study file that is kept in a locked filing cabinet on their respective premises. The original records will be maintained at the respective test sites.

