Subjects' identities will be kept confidential by assigning each subject a subject ID upon acceptance into the study. The subject ID will comprise the investigator's two initials (first and last name initials) and a three-digit number that will be based upon the subject's order of entry into the clinical study. For example, with Principal Investigator [name] would have a subject ID of JB101-JB110. Neither the study Sponsor nor Regulatory Insight, Inc. will receive any additional identifying information about a subject and will therefore have no way of linking a subject ID to a particular subject and his or her results.

MONITORING OF THE CLINICAL STUDY

Prior to commencement of the study, the trained study Monitor(s) will provide formalized and documented training to the conduct of clinical studies in general, to the specifics of the current clinical study protocol, to the identification and reporting of adverse events and protocol deviations and to the correct set-up, operation and treatment application of the Erchonia® HLS to the study population for all study staff involved parties. A formalized Clinical Trial Monitoring Plan will be in place for real time, remote and on-site monitoring, as applicable, that will be strictly followed to ensure on-going compliance and accuracy of procedures at the test site(s).

STATISTICAL ANALYSIS

As this is an observational pilot study only, there are no pre-established primary or secondary outcome measures and no pre-established individual subject or study success criteria; rather it is the goal of this study to explore the potential benefits of low level laser therapy administration with the Erchonia HLS™ in reducing symptoms related to tinnitus, the results of which may be used to assist in developing a controlled clinical study to formally evaluate the study goal in the future.

Outcomes Evaluated

The following outcomes will be evaluated as recorded across study duration:

- Tinnitus Handicap Inventory (THI)
- Numerical Rating Scale (NRS): Tinnitus Loudness
- Numerical Rating Scale (NRS): Tinnitus Annoyance
- Satisfaction Rating

Co-Variate Evaluation

Consideration will be given to the role of demographic variables and procedure group assignment.

Evaluation Time Points

Evaluation time points are baseline (pre-treatment), two weeks, four weeks, and 8 weeks study endpoint.

Statistical Procedures

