Outcome data will be presented descriptively and through trending. One-way ANCOVA analysis to evaluate the change in measurements across evaluation points may be applied, as applicable.

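### Does leaving the optional ANCOVA open, with groups assigned by the investigator, put the pilot's conclusions at risk?

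*Combined protocol and SAP*

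**What the plan says.** The Study Design section describes the trial in these terms: "This pilot study is a non-blinded, two-group evaluation of the effect". All ten subjects receive the active device, and the groups differ only in where it is applied. Under Non-Randomized, "The Investigator will assign 5 subjects to Group A and 5 subjects to Group B". Subject Group Assignment adds the timing: "A fully qualified subject is assigned by the investigator to Procedure Group A or to Procedure Group B". Qualification includes a THI total of "38 (Grade 3) or greater" and both NRS scores at 40 or more, so those scores are known before the group is chosen.

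Expected Results looks for change over time: "compared with baseline, subjects will show a reduction in tinnitus symptoms at study endpoint evaluation". The 8 Week Evaluation section agrees: "These recordings will form the study endpoint data set from which change from baseline will be evaluated with respect to assessing study outcome".

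The Statistical Analysis section disclaims pre-set outcome measures and success criteria and describes the aim as exploratory. Of covariates it says: "Consideration will be given to the role of demographic variables and procedure group assignment". The recorded demographics are age, gender and ethnicity. After descriptive presentation and trends, one model is offered: "One-way ANCOVA analysis to evaluate the change in measurements across evaluation points may be applied, as applicable".

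**The concern.** A design with two groups invites a comparison of the two, yet procedure group appears in the analysis only as something to consider. The ANCOVA's factor is not named outright, no covariate set is fixed, and the baseline score, which is the usual covariate for a change analysis, is not mentioned. An unblinded investigator who already holds the qualifying scores chooses the group. The groups could therefore start at different severities, and an analyst could pick, after seeing the data, the model that gives the more attractive contrast between application areas. The results may help design a controlled study, so a misleading contrast could influence which area is taken forward.

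**Working it through.** **1. The factor.** Expected Results, the 8 Week Evaluation and the ANCOVA sentence all speak of change from baseline or across visits. The natural reading takes evaluation point as the factor, with group and demographics as candidate covariates. No A-versus-B contrast is stated anywhere. The rest of the check asks what would happen if one were reported anyway.

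**2. Inputs.** From the documents: 5 + 5 = 10 subjects; THI range 0 to 100 with an entry floor of 38; visits at baseline and weeks 2, 4 and 8. The documents give no SD, correlation, alpha or power, so there is no sample-size calculation to reproduce. Assumed: correlation r between baseline and week 8 of 0.5, 0.7 or 0.8; equal SDs at both visits, so the slope b equals r; baseline THI SD of 15 points where points are needed; no true group effect.

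**3. Gap between the two estimates.** Let D0 and D8 be the A-minus-B differences at baseline and week 8.
- Unadjusted difference in change: D8 - D0.
- Baseline-adjusted difference: D8 - b × D0.
- Adjusted minus unadjusted: (1 - b) × D0.

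For D0 = 10 THI points: 0.5 × 10 = 5, 0.3 × 10 = 3 and 0.2 × 10 = 2 points.

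The entry floors do not alter this. Selecting on the baseline score leaves the slope unchanged in a linear model. With r = 0.8 and the baseline cut at its mean, the slope stays at 0.80, while the SD ratio rises to 1.28 and r falls to 0.63.

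**4. Which estimate is in error.** This comes from 200,000 simulated 5 v 5 trials per setting, in baseline SD units, with results listed for r = 0.5 / 0.7 / 0.8.

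| How the groups differ at baseline | Mean error, unadjusted | Mean error, adjusted | RMSE, unadjusted | RMSE, adjusted |
|---|---|---|---|---|
| By chance (random assignment) | 0 | 0 | 0.63 / 0.49 / 0.40 | 0.59 / 0.49 / 0.41 |
| Observed scores 1 SD apart | -0.50 / -0.30 / -0.20 | 0 | 0.74 / 0.54 / 0.43 | 0.65 / 0.54 / 0.45 |
| Stable severity 1 SD apart | 0 | +0.50 / +0.30 / +0.20 | 0.63 / 0.49 / 0.40 | 0.85 / 0.64 / 0.52 |

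Adjustment helps in some rows and harms in others. A rule fixed in advance would have no clear winner to name.

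**5. How often the estimates disagree.** Under random assignment they have opposite signs in about 17 / 14 / 12% of trials. With an imposed 1 SD imbalance this rises to 33 / 27 / 24% (observed scores) and 30 / 25 / 22% (stable severity). Chance alone produces an imbalance above 1 SD in 11% of trials. These are signs of a null difference, so they mostly reflect noise. The two 95% intervals disagree about excluding zero in only 4 to 5% of trials under random assignment.

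**6. Precision.** The median 95% half-width of the unadjusted A-B difference in change is t(8) × sqrt(2(1 - r) × 2/5) × sqrt(median chi-square(8)/8) = 1.40 / 1.08 / 0.88 SD. At SD 15 that is 1.40 × 15 = 21, 1.08 × 15 = 16 and 0.88 × 15 = 13 points, against gaps of 5, 3 and 2 points. The data cannot settle b either: its median half-width is 0.72 / 0.59 / 0.50.

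The pooled paired change in all ten subjects, which is what the plan sets out to describe, has half-width t(9) × sqrt(2(1 - r)/10) × sqrt(median chi-square(9)/9) = 0.69 / 0.53 / 0.44 SD. It involves no A-B contrast.

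**The case for a change.** The strongest case for a change is that two application areas were built into the design, so readers will compare them whatever the plan says, and the results may shape a controlled study. The reason for each assignment is hard to reconstruct later, and it decides which estimate is in error. Writing down the model, recording the basis of assignment and reporting both estimates would cost only a few sentences.

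Parts of this stand. No assignment rule is given, the scores are known beforehand, the baseline score is not named as a covariate, and the two estimates can diverge. But the proposed wording would not identify a better analysis. It would report both figures and concede that the pilot cannot choose between them. Nor would a recorded reason for assignment make five against five informative, given half-widths of about 0.9 to 1.4 SD. The caution it would add, that neither figure supports a conclusion, already follows from a plan that is exploratory, descriptive and without success criteria. It would also be too strong to say that the plan names no covariates: it lists demographics and group as candidates. What is missing is a fixed set.

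**Conclusion.** No change is needed. The analysis text is thin, but following it as written does not produce a wrong result. The visit-by-visit description and the pooled change from baseline do not depend on the open choice, the ANCOVA is optional, and no decision rests on an A-versus-B difference. Baseline THI and NRS scores are collected at qualification, so an analyst can tabulate them by group and, if the areas are compared, show the difference with and without baseline adjustment as description only. If the basis of assignment goes unrecorded, that is a limitation on any such comparison, in addition to the lack of randomization and blinding that the protocol already declares.

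The size is modest: a gap of 2 to 5 THI points for a 10-point imbalance, against 95% half-widths of about 13 to 21 points. These figures assume slopes of 0.5 to 0.8, equal SDs at the two visits, a THI SD of 15 and no true group effect, none of which the documents supply. Lower slopes would widen the gap (7 points at 0.3), but they would also widen the interval for the unadjusted difference.

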REDUCING TINNITUS SYMPTOMS**

THIS STUDY INVOLVES 8 WEEKS OF SELF-ADMINISTERED LASER LIGHT PROCEDURES WITH THE ERCHONIA® HLS™ LASER AT YOUR HOME

FOR MORE INFORMATION PLEASE CONTACT:

<PI name>
<test site name & location>
<phone # and/or e-mail>

b) Newspaper Ad

**Tinnitus
Research Study**

This study is to see if the Erchonia® HLS™, a non-invasive, investigational device that uses low-level laser light, can help to relieve tinnitus that has been ongoing for at least 6 months.

The study involves 8 weeks of self-administered at home treatments.

Please contact <PI name> at
<test site name & location> at
<phone and/or e-mail> for details.

Compensation

A subject will not receive financial compensation for his or her participation in this clinical study.

A subject will not be charged for the cost of the study procedures with the Erchonia® HLS™ Laser or for the cost of any other directly-related evaluations or measurements that occur as part of his or her participation in the study.

Sample size

There will be 10 qualified subjects enrolled in this pilot study, all receiving active procedures. 5 subjects will be assigned to Group A and 5 subjects to Group B.

STUDY PROCEDURE

STUDY TEST BATTERY

The following is a list and description of the study assessment tools to be used and the variables to be recorded in this clinical study. At each evaluation point, the precise tools and variables from this list that will be employed will be specified.

BASELINE VARIABLES

A. *Tinnitus Variables*

- Diagnosed etiology of tinnitus, if known. *Responses:* presbyacusis, noise-induced, unknown.
- Number of months/years since tinnitus onset.
- Location of tinnitus. *Responses:* unilateral - right ear, unilateral - left ear, bilateral - both ears, nonspecific (generally inside the head).

B. *Medication and Treatment*

- *Prior treatment approaches for tinnitus reduction:* Record all prior treatments, whether conventional or alternative, tried by the subject for tinnitus reduction.
- *Concomitant Medication and Therapy Use:* Record all over-the-counter and prescription medications currently used for any indication (other than the management of tinnitus symptoms)

C. *Subject Demographics:* Subject age, gender and ethnicity are recorded.

OUTCOME ASSESSMENT TOOLS

PRIMARY OUTCOME MEASURE:

Tinnitus Handicap Inventory (THI)

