2 WEEK EVALUATION

Following 2 weeks of study procedure administrations with the Erchonia® HLS™, the following will be recorded over videoconference or telemedicine with the site investigator and subject:

- Numerical Rating Scale (NRS): Tinnitus Loudness
- Numerical Rating Scale (NRS): Tinnitus Annoyance
- Tinnitus Handicap Inventory (THI)
- Adverse Events Evaluation

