4 WEEK EVALUATION

Following 4 weeks of study procedure administrations with the Erchonia® HLS™, the following will be recorded over videoconference or telemedicine with the site investigator and subject:

- Numerical Rating Scale (NRS): Tinnitus Loudness
- Numerical Rating Scale (NRS): Tinnitus Annoyance
- Tinnitus Handicap Inventory (THI)
- Adverse Events Evaluation

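### The optional one-way ANCOVA of change across visits has no within-subject term, although the same 10 subjects are scored four times; the resulting error depends on the layout, and the fix is wording only

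*Combined protocol and SAP*

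**What the plan says.** The Statistical Procedures paragraph under STATISTICAL ANALYSIS has two sentences. The first commits to descriptive presentation and trending. The second reads: "One-way ANCOVA analysis to evaluate the change in measurements across evaluation points may be applied, as applicable". It does not name the response, the factor, the covariate, the rows or the error term. The Co-Variate Evaluation paragraph mentions only demographics and procedure group.

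The readings are repeated. Under Evaluation Time Points: "Evaluation time points are baseline (pre-treatment), two weeks, four weeks, and 8 weeks study endpoint". The 2 Week and 4 Week Evaluation sections each record THI and both NRS scores, as does the 8 Week Evaluation. The pre-treatment readings that the protocol describes are those taken at qualification (Inclusion Criteria Part 2), for example "Total THI score is 38 (Grade 3) or greater". On sample size: "There will be 10 qualified subjects enrolled in this pilot study, all receiving active procedures". They are split 5 and 5 between Groups A and B by the investigator.

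The question asked is a within-subject one. Expected Results says "it is anticipated that compared with baseline, subjects will show a reduction in tinnitus symptoms at study endpoint evaluation", and the 8 Week Evaluation section describes the "study endpoint data set from which change from baseline will be evaluated with respect to assessing study outcome".

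The STATISTICAL ANALYSIS section also states that the study is an observational pilot with no pre-established outcome measures or success criteria, and that its results may help in developing a controlled study.

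**The concern.** A one-way ANCOVA treats its rows as independent. Evaluating change across evaluation points suggests several rows per subject, and these are not independent. The sentence leaves the layout open, and the possible layouts fail in different directions:

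- With raw scores by visit, differences between subjects go into the error term and a real fall can be missed.
- With a group term, or a mean change pooled over visits, repeated rows count as extra subjects and chance findings multiply.
- With one week-8 row per subject, the model is sound but answers a different question, Group A against Group B.

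At stake is how precisely the pilot reports its within-subject change, and how an A-versus-B difference is read when a later controlled study is designed.

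**Working it through.** **Inputs from the documents.** 10 subjects (5 + 5); 4 readings each, so 40 raw rows or 30 change-from-baseline rows. The plan gives no alpha, SD, correlation or sample-size calculation, so there is no stated figure to reproduce.

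**Assumptions.** Two-sided alpha 0.05, normal scores, unit SD at every visit, complete data, no true change and no true group difference. Within-subject correlation ρ is taken as equal for all visit pairs (0.3, 0.5, 0.7, 0.8). Serial correlation was also tried: adjacent-visit 0.3-0.8, or decay by elapsed weeks with a two-week correlation of 0.8-0.95. Rates come from simulation, with 20,000 to 40,000 runs per setting for most models and 4,000 for some change-score models. Where separate runs differ slightly, the range is shown.

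**Step 1: 40 raw rows, visit as factor.** The true variance of the week-8 minus baseline mean is 2(1−ρ)/10. The model uses 2/10. The model SE is therefore 1/√(1−ρ) times the true one: 1.20, 1.41, 1.83 and 2.24. At ρ = 0.5 the nominal 95% interval is about 2 × 2.028 × √(2/10) = 1.81 SD wide, against 2 × 2.262 × √(1/10) = 1.43 SD for a paired t interval. The simulated averages, 1.79 and 1.39, are slightly smaller because the sample SD averages a little below 1.

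**Step 2: group term on several rows per subject.** On 40 rows the subject mean has variance (1+3ρ)/4 and the model uses 1/4. The SE ratio is 1/√(1+3ρ): 0.73, 0.63, 0.57 and 0.54. On 30 change rows adjusted for baseline, a subject's rows have residual correlation r = ρ/(1+ρ). The SE ratio is 1/√(1+2r): 0.83, 0.77, 0.74 and 0.73.

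**Step 3: mean change pooled over 30 rows.** Each change has variance 2(1−ρ), and two changes from one baseline have covariance 1−ρ. Their correlation is 0.5 whatever ρ is, so the SE is about 1/√(1 + 2 × 0.5) = 0.71 of the true one.

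**Step 4: week-8 interval from 30 change rows.** The week-8 mean uses one row per subject, so correlation between rows does not enter its variance, 2(1−ρ)/10.
- Without a baseline covariate, under equal correlation, the pooled residual variance is also 2(1−ρ). The SE is right on average and only the degrees of freedom are overstated.
- With centred baseline added, the residual variance falls to 1−ρ², and the sampling error of the baseline mean is ignored. The SE ratio is √((1+ρ)/2): 0.81, 0.87, 0.92 and 0.95.
- Under serial correlation the variance of change grows with time but is pooled. With adjacent-visit correlation 0.5 the variances are 1.00, 1.50 and 1.75, averaging 1.42. The week-8 SE ratio is √(1.42/1.75) = 0.90.

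**Results, equal correlation**

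| Quantity | ρ=0.3 | 0.5 | 0.7 | 0.8 |
|---|---|---|---|---|
| 40 rows: true size of time test, % | 1.4-1.6 | 0.4-0.5 | 0.06-0.13 | 0.01 |
| 40 rows: week-8 CI width, SD | 1.80 | 1.79 | 1.78 | 1.78 |
| Paired t: week-8 CI width, SD | 1.65 | 1.39 | 1.08 | 0.88 |
| 40 rows: group false positives, % | 16 | 22-23 | 28-29 | 31 |
| 30 rows: group false positives, % | 10-11 | 13-15 | 16 | 16-17 |
| 30 rows: pooled change false positives, % | 17-18 | 17-18 | 17-18 | 17-18 |
| 30 rows, no covariate: week-8 coverage, % | 94-95 | 94-95 | 94-95 | 94-95 |
| 30 rows, centred baseline: week-8 coverage, % | 89 | 90-91 | 92 | 93 |

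**Serial correlation.** Week-8 coverage from 30 change rows is 86-93% without the covariate and about 84-86% with it. The directions in Steps 1 to 3 do not change.

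**Step 5: one week-8 row per subject, change on group and baseline.** The size is about 5%, so no within-subject term is needed. The term tested is A versus B, with a 95% CI 3.0, 2.7, 2.2 and 1.9 SD wide at the four correlations.

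**Reference.** The paired t interval for week-8 change covers about 95% in every setting.

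**The case against.** The strongest reply is that little depends on the sentence. It is doubly permissive, the committed analysis is descriptive, and no alpha, decision or success criterion rests on the ANCOVA. Nothing says that subject will be ignored, and a one-row-per-subject ANCOVA is valid. The layouts checked here are constructions: baseline score is not among the named covariates, and the raw-score model without a covariate is strictly an ANOVA. All of this stands, and it makes the point minor. It does not remove it. The one valid layout does not address the change from baseline that the protocol sets out to evaluate, and no other inferential method is named.

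Two stronger readings are tempting, and neither is supported.

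- A reader might infer that repeated rows always make the week-8 change interval too narrow because a subject's rows are correlated. Under equal correlation the 30-row interval without a covariate is close to nominal. A regression of week-8 change on centred baseline with only one row per subject still covers just 90-94%. The shortfall therefore comes mainly from the ignored baseline sampling error and, under serial correlation, from pooling unequal variances.
- A reader might infer that a chance group difference will decide the treatment area for the next study. No passage sets such a rule. With 5 subjects per group, assigned by the investigator, no choice of error term would make that comparison reliable.

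**Conclusion.** The point holds as a minor one. The only inferential method named omits the within-subject structure of the data and leaves the layout open. On 40 raw rows the time test is far too conservative and the week-8 interval is wider than a paired one. A group term on either multi-row layout, or a mean change pooled over 30 rows, is anticonservative. The week-8 interval from 30 change rows is about right in one case and too narrow in others. The one-row layout is valid but tests A against B.

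The sizes rest on assumed correlations, normality and complete data, none of which the documents supply. The directions for the time, group and pooled-change tests held at every positive correlation tried. The documents do not support saying that the plan commits to an invalid analysis or that its descriptive results are affected.

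**What to change.** Replace the ANCOVA sentence with:

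> For THI, NRS Loudness and NRS Annoyance, the mean within-subject change from baseline to Week 8 will be reported with a 95% CI from a paired analysis, as exploratory. Any analysis using several visits per subject will account for the repeated measures (subject effect with a sphericity correction, or a serial covariance). Any Group A versus B comparison will use one Week 8 value per subject, adjusted for baseline, as exploratory.

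The correction or serial covariance is needed because a plain subject block gives a time-test size of 5.4-7.1% when adjacent-visit correlation is 0.3-0.9. A random-intercept interval then covers only 86-93% in the serial settings tried.

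The cost is wording only, with no new data, visits or subjects. There is a small downside. If correlation really is equal across visits, the paired interval is slightly wider than a random-intercept model would give: 1.65, 1.39, 1.08 and 0.88 SD against 1.52, 1.28, 1.00 and 0.81 SD at correlations 0.3, 0.5, 0.7 and 0.8.

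The paired interval describes observed change. With no control group and an eligibility floor on the baseline scores, which invites regression to the mean, it should not be labelled a device effect.
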